5.8.1 Early Withdrawal from the Study

Criteria for discontinuation of Study Drug can be found in [Section 4.3](#).

Patients may be withdrawn from the study for a number of reasons, including those outlined below.

- Withdrawal of consent for all study procedures
 - Patients withdrawing their consent for all study procedures must be given the option to continue to give consent for passive follow-up (i.e. by means of chart review) for adverse events through Study Week 24.
- Discontinuation of the study by the Sponsor

6 DRUG SUPPLIES AND DOSING

6.1.1 *Dosing and Administration*

The dose of COR-001 for intravenous (IV) administration must be prepared using aseptic techniques. Drug Product is presented as a single use vial and any unused portion must be discarded.

COR-001 is supplied as a lyophilised cake. Reconstitution with 1.2 mL Sterile Water for Injection gives a 1.0 mL nominal volume containing 50 mg of COR-001 (50mg/mL COR-001 stock solution) in 25 mM L-histidine/L-histidine hydrochloride monohydrate, 225 mM (8.5% [w/v]) trehalose dihydrate, 0.05 % (w/v) polysorbate 80, pH 6.0.

The planned doses for the study are described in [Section 3.5.4](#) and in [Table 2](#). The actual doses will be based on a review of safety and in-life pharmacokinetic data (to the extent available) during the study. The reconstituted COR-001 stock solution will require serial dilution in IV Bag Protectant (IVBP) to obtain concentrations which permit manageable volumes of drug to be handled. Please see [Table 2](#) and [Figure 3](#). Personnel responsible for study drug preparation should have an appropriate background (i.e., physician, pharmacist, pharmacy technician, nurse, or other personnel approved by the Sponsor) and has been appropriately trained. Please see Pharmacy Manual for full details.

The final required volume of diluted COR-001 (1.6-18.mL) plus IV Bag Protectant (1.8 mL) is added to 100 mL 0.9% saline for IV infusion ([Figure 3](#)).

Each dose of COR-001 or placebo will be administered via IV infusion with a 0.2 micron in-line filter over approximately 60 minutes, starting any time prior to the last 1 hour of dialysis. Study Visits during which Study Drug infusions are required should be planned on the same day of the week so that Study Drug administration can occur on a schedule of every 14 days. Please see the Pharmacy Manual for instructions on preparing and administering the Study Drug and storage of prepared Study Drug.

Special Situations

- If the dialysis treatment is ended earlier than planned, continue the Study Drug infusion until the infusion is completed.
- If the infusion is interrupted or flow rate slowed (e.g., due to an adverse event) and dialysis is completed before the Study Drug infusion has ended, continue the Study Drug infusion until the infusion is completed.
- Patients who require slower flow rates (e.g., due to prior intolerance with the normal flow rates), the Study Drug administration may be started earlier in the dialysis session to allow the Study Drug infusion end to coincide with the end of dialysis or prior to the end of dialysis.

- Patients who miss a dose of Study Drug (e.g., due to a missed dialysis visit) may receive the missed Study Drug up to 96 hours later (on a dialysis day). If the missed dose cannot be administered within this time frame, the dose should be considered “missed” and the next dose administered at the next study visit as planned.

For patients for whom logistical considerations require minor adjustments to the Study Drug infusion timing (including administration of the Study Drug prior to or after dialysis), please contact the Medical Monitor.

[figure not shown]
In the above special situations, please ensure that blood testing that is timed with the start and end of infusion are adhered to.

Table 2 Planned COR-001 Doses, Serial Dilutions and Administered Volumes

[figure not shown]
Dose Cohort	Dosing Regimen	Drug Stock Concentration (mg/mL in sterile water)	# of serial dilutions (1 ml drug stock added to 2 ml from dilution vial for final volume of 3 ml)	Diluted Drug Volume to be Used (mL)	IVBP volume to be added to saline infusion bag (in 100 ml saline)	Total Volume to be added to 100mL 0.9% saline
1	2 mg every 14 days	50	3	1.1	1.8	2.9
2	6 mg every 14 days	50	2	1.1	1.8	2.9
3	20 mg every 14 days	50	1	1.2	1.8	3.0
4	60 mg every 14 days	50	0	1.2 (0.6 mL from 2 drug vials)	1.8	3.0
As of Protocol Amendment 3, the actual doses (all given every 14 days) were 2 mg (Cohorts 1 and 4); 6 mg (Cohorts 2 and 3); 20 mg (Cohort 5).						

Figure 3 A and B: Reconstitution and Serial Dilution of COR-001 for Administration

3A: Reconstitution of COR-001 for Administration for Cohorts 1-3

3B: Reconstitution of COR-001 for Administration for Cohort 4

The date and time of administration of Study Drug must be recorded in the appropriate sections of the CRFs. Any interruptions in the investigational product infusion (date and time infusion was stopped and date and time infusion was restarted) and any changes in flow rate should also be documented in the CRF with an appropriate explanation.

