²If the MTD is exceeded, a lower dose, including previously studied dose, may be selected.

The planned doses shown here may be adjusted based on accruing data. The highest dose that will be studied is a cumulative dose of 360 mg. Expansion cohorts to further evaluate doses below the dose that exceeded the MTD may be initiated at any time.

Table 1 Planned COR-001 Doses, Serial Dilutions and Administered Volumes

DOSE COHORT	DOSING REGIMEN	DRUG STOCK CONCENTRATION (MG/ML IN STERILE WATER)	# OF SERIAL DILUTIONS (1ML DRUG STOCK ADDED TO 2ML DILUTION VIAL FOR FINAL VOLUME OF 3ML)	DILUTED DRUG VOLUME TO BE USED (ML)	IVBP VOLUME TO BE ADDED TO SALINE INFUSION BAG (IN 100ML SALINE)	TOTAL VOLUME TO BE ADDED TO 100ML 0.9% SALINE
1	2 mg every 14 days	50	3	1.1	1.8	2.9
2	6 mg every 14 days	50	2	1.1	1.8	2.9
3	20 mg every 14 days	50	1	1.2	1.8	3.0
4	60 mg every 14 days	50	0	1.2 (0.6ml from 2 drug vials)	1.8	3.0

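### Protocol Section 6.1.1 prints a garbled diluted-drug volume range that does not overlap the 1.1-1.2 mL in Protocol Table 2 and SAP Table 1 for the same preparation step

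*Protocol*

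**What the plan says.** Protocol Section 6.1.1 (Dosing and Administration) describes reconstitution, serial dilution and addition to the infusion bag. One reconstituted vial "gives a 1.0 mL nominal volume containing 50 mg of COR-001 (50mg/mL COR-001 stock solution"). For the last step the text says: "The final required volume of diluted COR-001 (1.6-18.mL) plus IV Bag Protectant (1.8 mL) is added to 100 mL 0.9% saline". It gives one range for the whole study, with no volume for any particular dose level and no number of dilutions. It refers the preparer to Table 2, Figure 3 and the Pharmacy Manual.

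Protocol Table 2, in the same section, gives a volume for each dose level. Its dilution column is headed as the number "of serial dilutions (1 ml drug stock added to 2 ml from dilution vial for final volume of 3 ml"). The diluted drug volumes are 1.1 mL for the 2 mg and 6 mg levels and 1.2 mL for the 20 mg level. For the 60 mg level the entry is "1.2 (0.6 mL from 2 drug vials"). Every row adds 1.8 mL of bag protectant, and the total-volume column reads 2.9, 2.9, 3.0 and 3.0 mL.

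Table 1 in SAP Section 1.3.1 carries the same volumes, with "1.2 (0.6ml from 2 drug vials") at the top level.

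The Protocol Synopsis and Section 3.2 cap the cumulative dose at 360 mg, which is six doses of 60 mg.

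**The concern.** Two parts of one section give different volumes for one preparation step, and neither is named as controlling. The ranges do not overlap. The conflict does not depend on how the misprinted upper limit is read, because the lower limit alone lies above every table entry.

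Dose is the experimental factor in this study. Escalation, the DLT count against the MTD rule and the by-dose pharmacodynamic summaries all assume that the nominal dose was given. SAP Section 2.2 also removes patients with two or more incorrect doses from the pharmacodynamic population, and it classes a patient who did not receive the assigned dose by the highest dose received. Both rules need an unambiguous definition of a correctly prepared dose.

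**Working it through.** **Inputs.** The stock is 50 mg/mL (Protocol Section 6.1.1). Each dilution is 1 mL into 2 mL, a factor of 3 (Table 2 column heading). The numbers of dilutions k are 3, 2, 1 and 0, and the table volumes are 1.1, 1.1, 1.2 and 1.2 mL (Table 2). The legible text volume is 1.6 mL (Section 6.1.1). An upper limit of 1.8 mL is an assumed reading of the misprint.

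**Formula.** Concentration = 50 / 3^k mg/mL. Dose = concentration × volume.

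**Step 1: reproduce the planned doses from Table 2.**

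| Planned dose | k | Concentration (mg/mL) | Table 2 volume (mL) | Dose from Table 2 volume (mg) | Volume giving the exact dose (mL) |
|---|---|---|---|---|---|
| 2 mg | 3 | 1.852 | 1.1 | 2.04 | 1.08 |
| 6 mg | 2 | 5.556 | 1.1 | 6.11 | 1.08 |
| 20 mg | 1 | 16.667 | 1.2 | 20.0 | 1.20 |
| 60 mg | 0 | 50 | 1.2 | 60.0 | 1.20 |

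The largest departure is 1.9% (2.037 against 2, and 6.111 against 6). The total-volume column also adds up: 1.1 + 1.8 = 2.9 and 1.2 + 1.8 = 3.0. With the text volume the total would be at least 1.6 + 1.8 = 3.4 mL.

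**Step 2: keep Table 2's dilution counts and substitute the text volume.**

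| Planned dose | Dose at 1.6 mL (mg) | Excess over Table 2 volume | Dose at 1.8 mL, assumed (mg) | Excess over Table 2 volume |
|---|---|---|---|---|
| 2 mg | 2.96 | 1.6/1.1 − 1 = 45% | 3.33 | 1.8/1.1 − 1 = 64% |
| 6 mg | 8.89 | 45% | 10.0 | 64% |
| 20 mg | 26.7 | 1.6/1.2 − 1 = 33% | 30.0 | 1.8/1.2 − 1 = 50% |
| 60 mg | 80.0 | 33% | 90.0 | 50% |

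**Step 3: compare with the cumulative maximum.** At the top level, 6 × 80 = 480 mg and 6 × 90 = 540 mg, against 6 × 60 = 360 mg.

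**The case against.** The best defence is that the sentence in Section 6.1.1 cannot be followed on its own. It has no dilution count and no volume per dose level, so a preparer must go to Table 2, where the dilution count and the volume stand in the same row. The doses in Step 2 arise only if someone takes the count from that row and the volume from the prose. The section also defers to Figure 3, which is not shown in the text reviewed, and to the Pharmacy Manual, which was not supplied. Those sources may leave sites in no doubt. This stands, and it makes the dose differences conditional. It does not remove the conflict, because the section prints both volumes and names neither as controlling.

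The range may also be left over from a superseded schedule. The Amendment 1 summary lists former weekly doses of 1, 3, 10 and 30 mg. With 4, 3, 2 and 1 dilutions (assumed, not documented), the required volumes are 1/(50/81) = 1.62, 3/(50/27) = 1.62, 10/(50/9) = 1.80 and 30/(50/3) = 1.80 mL. This would explain both ends of the range, but it is inference only. If it is right, the sentence still stands uncorrected in the current protocol.

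Three stronger readings are tempting, and the documents support none of them:

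- **That patients received the wrong dose.** No dosing record is among the documents. Section 13.8 requires accountability records that include stock-solution volumes, and Section 11.4.6.1 summarises serum concentrations by dose group, so the point can be checked.
- **That the text permits 18 mL, some 15 to 16 times the table volume.** A dilution vial has a final volume of 3 mL, and the two vials at the top level hold 1.0 mL nominal each. Eighteen mL cannot be drawn from either, so the figure is a misprint and not a dose that could be given.
- **That the mismatch alters the dose cap.** The cap is stated in milligrams and does not depend on volume. The 480-540 mg figure is what the text volumes would imply at the 60 mg level. That level was not among the doses listed as actually given as of Amendment 3, which were 2, 6 and 20 mg.

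**Conclusion.** The inconsistency is real and is in current text. Section 6.1.1 and Protocol Table 2 (with SAP Table 1) give volumes for one step that do not overlap, and only the table volumes reproduce the planned doses, to within 2%. That is a finding about internal agreement; this review does not say which volume is right.

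If the text volume were combined with Table 2's dilution counts, the dose would exceed that from the table volumes by 33-45% at 1.6 mL. The further 50-64%, and the 540 mg end of the cumulative range, rest on the added assumption that the upper limit means 1.8 mL. The text assigns no volume to any dose level, so these are conditional sizes and not estimates of what was delivered. No calculation in the plan is wrong; the fault lies in a preparation instruction. In a dose-escalation trial that still has to be put right.

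**What to change.** Reconcile the volume range in Section 6.1.1 with Table 2, Figure 3, SAP Table 1 and the Pharmacy Manual, so that one diluted-drug volume per dose level appears everywhere. The simplest way is for Section 6.1.1 to refer to a single table and give no separate range.

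For the cohorts already dosed, confirm from the drug accountability records which volume was used. Section 13.8 specifies stock-solution volumes. If those do not show the diluted volume drawn, the site preparation records should be consulted. Any departure should be carried into the SAP Section 2.2 rules on incorrect doses and dose classification.

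The cost is one wording correction to the protocol and a pharmacy record check. No design, sample size or analysis method changes.

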6.1.2 Storage

COR-001, placebo, diluent, and the IV bag protectant must be stored at 2 to 8°C in the original container and must not be frozen.

6.1.3 Formulation and Packaging

Table 3 Composition for COR-001 for Injection, 50 mg/Vial

Ingredients	Quantity per vial
COR-001	50 mg
L-Histidine	1.9 mg
L-Histidine hydrochloride monohydrate	2.6 mg
Trehalose dehydrate	85.0 mg
Polysorbate 80	0.5 mg
Water for Injection	1.2 mL reconstitution volume

Table 4 Composition for Placebo for Injection (3 mL vial)

Ingredients	Quantity per vial
L-Histidine	1.9 mg
L-Histidine hydrochloride monohydrate	2.6 mg
Trehalose dehydrate	85.0 mg
Polysorbate 80	0.5 mg

Table 5 Composition IV Bag Protectant and Diluent (3 mL vial)

Ingredients	Quantity per vial
Sodium citrate	11.3 mg
Citric acid	1.2 mg
Polysorbate 80	139.1 mg

6.2 Drug Accountability and Compliance

The dispensing pharmacist or designated qualified individual will write the date dispensed, dose dispensed, and the patient’s identification number, and initials on the Drug Accountability Source Documents. All medication supplied will be accounted for on the

Drug Accountability Record. All partially used or unused drug supplies will be destroyed at the site in accordance with approved written site procedures, or returned to Corvidia Therapeutics only after written authorization is obtained from Corvidia Therapeutics. The Investigator will maintain a record of the amount and dates when unused supplies were either destroyed or returned to Corvidia Therapeutics. All records will be retained as noted in [Section 13.5](#).

7 PRIOR AND CONCOMITANT MEDICATIONS AND TREATMENTS

7.1 Prior Medications and Treatments

See [Section 4.1](#) and [Section 4.2](#) for restrictions on prior medications and treatments.

7.2 Concomitant Medications and Treatments

Patients may receive concomitant medications as clinically indicated with the following restrictions:

- Parenteral iron: For patients receiving IV or intradialytic iron, doses and frequency must be maintained during Study Weeks 1 through 24 (see [Appendix D](#))
- ESAs: Restrictions on dose adjustment during Study Weeks 1-4 and dose adjustments during Study Weeks 5 through 24 should be made in agreement with the protocol requirements and guidelines (see [Appendix D](#))
- Oral ferric citrate: For patients receiving this drug during Screening, maintain the dose during Study Weeks 1 through 24
- Systemic immunosuppressive drugs (i.e., such as cyclosporine, tacrolimus, sirolimus, mycophenolate, oral and intravenous glucocorticoids other than prednisone [or equivalent] up to a dose of 5 mg per day) may not be prescribed at any time during Study Weeks 1-24. Topical use (e.g., cyclosporine eye drops) is not restricted

Note: Use of otic, ophthalmic, inhaled, and topical corticosteroids or local corticosteroid injections are not restricted. Short-term systemic glucocorticoid use (e.g., less than 5 consecutive days) for managing acute illnesses is also not restricted.

- Narrow therapeutic window medications that are influenced by CYP enzymatic pathways (See list in [Appendix B](#)) may not be prescribed at any time during Study Weeks 1-24.
 - Warfarin is permitted, but the INR must be monitored closely and, at minimum, according to the protocol Schedule of Events (see [Appendix A](#))

8 MANAGEMENT OF SPECIFIC ADVERSE EVENTS

8.1 Serious Infections

Study drug treatments should be withheld if patients experience a serious infection until the infection is believed to have completely resolved. The Investigator should contact the Medical Monitor to discuss whether the patient should return to Study Drug treatment.

8.2 Infusion-Related Reactions, Hypersensitivity, and Anaphylaxis

Signs of a possible infusion-related reactions include fever, chills, pruritus, urticaria. Cardiopulmonary reactions including, but not limited to, chest pain, dyspnea, hypotension or hypertension may also be indicative of an infusion reaction, but some, such as hypotension may be difficult to distinguish from symptoms related to the dialysis procedure-related signs and symptoms. In these situations, Investigators must determine whether or not the symptom(s) represent an infusion-related reaction (e.g., by considering symptoms and symptom severity are typical for that patient, etc.).

Anaphylaxis is a severe, potentially fatal, systemic allergic reaction that occurs suddenly after contact with an allergy-causing substance, such as an investigational product.

For the purposes of this study, a hypersensitivity reaction is defined as an acute onset of an illness with involvement of the skin, mucosal tissue, or both during infusion of the Study Drug (but does not meet the definition of anaphylaxis described above).

If signs and symptoms of infusion-related reactions are observed during the infusion and the patient's cardiovascular status is stable:

- Reduce the flow rate of the infusion by at least half, and increase the infusion time.
- If the patient continues to show signs and symptoms of hypersensitivity, administer an IV dose of antihistamine, if the Investigator believes this is appropriate. The infusion may also be interrupted, if needed, and restarted at a flow rate that is at least 50% reduced.
- In patients who have experienced mild or moderate infusion reactions during prior Study Drug administrations, antihistamines and/or acetaminophen may be administered prophylactically prior to subsequent infusions, at the discretion of the Investigator.

In patients who experience severe (i.e., \geq Grade 3): infusion-related reactions, cardiopulmonary infusion reactions, anaphylaxis, or hypersensitivity (see definition and grading below):

- Permanently discontinue the Study Drug
- Treat the patients as for an anaphylactic reaction with IV antihistamines, corticosteroids, epinephrine, inhaled bronchodilators, and other measures as necessary

- Obtain a blood sample for the presence of anti-drug antibodies
- The patient should remain in the study for continued follow-up, but should receive no further Study Drug

CTCAE Grading for Infusion-Related Reactions

- Grade 1: Mild, transient reaction; infusion interruption not indicated; intervention not indicated
- Grade 2: Therapy or infusion interruption indicated but responds promptly to symptomatic treatment (e.g., antihistamine, non-steroidal anti-inflammatory drugs [NSAIDS], narcotics, IV fluids); prophylactic medications indicated for ≤ 24 hours
- Grade 3: Prolonged (e.g., not rapidly responsive to symptomatic medication and/or brief interruption of infusion); recurrence of symptoms following initial improvement; hospitalization indicated for clinical sequelae
- Grade 4: Life-threatening consequences; urgent intervention indicated
- Grade 5: Death

CTCAE Grading for anaphylaxis

- Grade 3: Symptomatic bronchospasm, with or without urticarial; parenteral intervention indicated; allergy-related edema/angioedema; hypotension
- Grade 4: Life-threatening consequences; urgent intervention indicated
- Grade 5: Death

9 ADVERSE EVENT REPORTING

9.1 Adverse Event Definitions

An AE is any undesirable event or any untoward medical occurrence that occurs to a participant during the course of a study, or the protocol-defined time after study termination, whether or not that event is considered Study Drug-related.

Examples include:

- Any treatment emergent signs and symptoms (events that are marked by a change from the patient’s baseline/entry status [e.g., an increase in severity or frequency of pre-existing abnormality or disorder]);
- All reactions from Study Drug, abuse of drug, withdrawal phenomena, sensitivity or toxicity to Study Drug;
- Apparently unrelated illnesses;
- Injuries or accidents (e.g., for a fall secondary to dizziness, record “dizziness” as the event and include the information about the fall in the comment/narrative section and information about any injury secondary to the fall as part of the “outcome”);
- Exacerbations (increase in frequency or severity) of symptomatology, subjective patient-reported events, new clinically significant abnormalities in clinical laboratory, physiological testing or physical examination;
- Abnormal laboratory findings considered by the Investigator to be clinically significant. In general, an abnormal laboratory value should not be recorded as an adverse event unless:
 - It is associated with clinical signs or symptoms,
 - Requires an intervention, results in a serious adverse event, or
 - Results in study termination or interruption/discontinuation of study treatment.

However, if none of the above apply, but the laboratory abnormality is considered clinically significantly worsened, it should be reported as a laboratory AE (e.g., “increased white blood cell count”). When recording an adverse event resulting from a laboratory abnormality, the resulting medical condition rather than the abnormality itself should be recorded (e.g., record “anemia” rather than “low hemoglobin”).

9.2 Serious Adverse Event Definition

An SAE is any AE, occurring at any dose and regardless of causality, that:

- Results in death;
- Is life-threatening. Life-threatening means that in the opinion of the Investigator or Study Sponsor, the patient was at immediate risk of death from the reaction as it occurred, (i.e., it does not include a reaction that hypothetically might have caused death had it occurred in a more severe form);
- Requires inpatient hospitalization or prolongation of existing hospitalization. Hospitalization admissions and/or surgical operations scheduled to occur during the study period, but planned before the signing for the ICF, are not considered AEs if the illness or disease existed before the patient was enrolled in the trial, provided that it did not deteriorate in an unexpected manner during the trial (e.g., surgery performed earlier than planned);
- Results in persistent or significant disability/incapacity. Disability is defined as a substantial disruption of a person's ability to conduct normal life functions;
- Is a congenital anomaly/birth defect;
- Is an important medical event. An important medical event is an event that may not result in death, be life-threatening, or require hospitalization but may be considered an SAE when, based upon appropriate medical judgment, it may jeopardize the patient and may require medical or surgical intervention to prevent one of the outcomes listed in the definitions for SAEs. Examples of such medical events include allergic bronchospasm requiring intensive treatment in an emergency room or at home, blood dyscrasias or convulsions that do not result in inpatient hospitalization, or the development of drug dependency or drug abuse.

A distinction should be made between the terms “serious” and “severe” since they **are not** synonymous. The term “severe” is often used to describe the intensity (severity) of a specific event (as in mild, moderate, or severe myocardial infarction); the event itself, however, may be of relatively minor medical significance (such as severe headache). This is **not** the same as “serious,” which is based on patient/event outcome or action criteria usually associated with events that pose a threat to a patient's life or functioning. A severe adverse event does not necessarily need to be considered serious. For example, persistent nausea of several hours duration may be considered severe nausea but not an SAE if the event does not meet the serious criteria. On the other hand, a stroke resulting in only a minor degree of disability may be considered mild, but would be defined as an SAE based on the above noted serious criteria. Seriousness (not severity) serves as a guide for defining regulatory reporting obligations.

